4. STUDY DESIGN

4.1 Overall design

This is an open-label, non-randomized, international, multicenter study investigating durvalumab in combination with tremelimumab followed by durvalumab monotherapy in pediatric patients from birth to <18 years of age with relapsed or refractory malignant solid tumors.

The study will be conducted in approximately 7 countries involving approximately 20 investigative centers. It was initiated in Q1 2019. The last-patient-last-visit for the final analysis is estimated to occur in Q1 2023.

This study will be conducted in 2 parts: a dose-finding phase (Phase I) followed by a disease specific expansion phase (Phase II). The purpose of this study is to identify the recommended Phase II dose (RP2D) that will be taken forward to determine preliminary antitumor activity of durvalumab in combination with tremelimumab in solid malignant tumors, using disease specific response criteria.

Table and Table lists the cohorts into which these malignancies will be grouped for both the dose-finding and dose-expansion phases of the study.

Table 6 **Disease cohorts for dose-finding phase**

Cohort	Type of cancer
SARC-1	Bone sarcomas: osteosarcoma or Ewing sarcoma
SARC-2	Soft-tissue sarcomas: rhabdomyosarcoma, non-rhabdomyosarcoma soft-tissue sarcoma, other sarcomas
NB	Neuroblastoma
STO	Other solid tumors (not represented in the other solid tumor cohorts)

Table 7 **Disease cohorts for dose-expansion phase**

Cohort	Type of cancer
SARCOMA	Bone sarcomas: osteosarcoma, Ewing sarcoma; Soft-tissue sarcomas: rhabdomyosarcoma, non-rhabdomyosarcoma soft-tissue sarcoma, other sarcomas
STO	Other solid tumors (not represented in the other solid tumor cohorts)

Note: Patients with soft-tissue sarcomas must account for $\geq 40\%$ of those enrolled in the SARCOMA cohort.

During the dose-finding phase (I), durvalumab will be given as monotherapy for 1 cycle followed by the addition of tremelimumab for the next 4 cycles. For the dose-expansion phase (II), durvalumab will be given in combination with tremelimumab for the first 4 cycles, starting on Cycle 1. When durvalumab is given in combination with tremelimumab, a maximum number of four 28-day cycles of tremelimumab will be permitted, followed by durvalumab monotherapy administered q4w. Study treatment will be administered until clinical or confirmed disease progression (determined by the Investigator against tumor-specific objective criteria) or until any of the other discontinuation criteria are met, whichever comes first. Tumor-specific objective response (OR) criteria are provided in [Appendix F](#) for NB, and [Appendix E](#) for solid tumors (Response Evaluation Criteria in Solid Tumors [RECIST 1.1]).

However, if in the opinion of the Investigator, a patient received clinical benefit from treatment with the combination of durvalumab and tremelimumab and subsequently progressed whilst on durvalumab maintenance monotherapy, such patients may restart treatment with the combination of durvalumab and tremelimumab for 4 cycles. A patient who meets these criteria should be reconsented and receive another 4 cycles of tremelimumab while continuing durvalumab treatment.

The immune-related Response Evaluation Criteria in Solid Tumors (irRECIST) are also provided in [Appendix G](#). Note: The incorporation of the irRECIST appendix in this protocol is only meant to serve as a supplement for treating physicians to help in their clinical decision-making in situations where tumor response, based on RECIST 1.1, is in doubt.

The study outline is provided in [Figure 1](#). The objectives and endpoints, as well as the projected number of patients who will participate in this study, including the assumptions underlying the sample size calculations, are provided in [Section 3](#) and [Section 9.2](#), respectively.

4.1.1 Dose-finding phase

The dose-finding phase of the study will be conducted using a modified 3 + 3 design to determine whether durvalumab and tremelimumab can be administered safely in children and if adult exposures can be achieved. Dose finding will only be assessed in patients with relapsed or refractory solid malignant tumors including osteosarcoma and Ewing sarcoma (SARC-1), rhabdomyosarcoma, non-rhabdomyosarcoma, and other sarcomas (SARC-2), NB, other solid tumors (STO). Starting doses of durvalumab and tremelimumab will be 100% of the recommended adult dose as a weight-adjusted dose administration. The dose-finding phase will seek to identify the RP2D for durvalumab monotherapy and durvalumab given in combination with tremelimumab. Pediatric patients with relapsed or refractory malignant solid tumors, will be enrolled and treated in 2 arms, based on patient weight: Arm A for patients ≥ 35 kg and Arm B for patients < 35 kg.

As seen in Section 4.3.1, available PK data are consistent with simulation-based predictions and indicate that administration of an adult weight-adjusted dose to children with body weight ≥ 35 kg will result in a PK profile very similar to the observed profile in adults. These findings also suggest that the target engagement and saturation are likely to be similar between adults and children. However, simulation-based predictions indicate that children with body weight < 35 kg will have exposures that are lower than the predicted profile in adults, thus requiring higher doses to reach adult equivalent exposures. Therefore, during the dose-finding phase of this study, the recommended adult weight-adjusted durvalumab and tremelimumab doses will be examined in 2 weight-based cohorts separated by a cutoff weight of 35 kg. Based on emerging data during the conduct of the study, cohorts may also be backfilled to provide further assessment of safety and PK in specific age groups and to ensure a broad representation of ages/weights at a given dose level (DL).

At least 1 patient representing each of the following pediatric age subsets will be enrolled: birth to 5 years, 6 to 11 years and 12 to < 18 years. However, patients under 2 years of age will only be enrolled after at least 3 pediatric patients older than 2 years of age have been dosed with durvalumab and tremelimumab and have cleared the DLT observation period and have been evaluated by the DRC. Additionally, at least 1 day between first patient and subsequent patients dosed at each DL is required.

Three DLs may be explored in each of the treatment arms (detailed DLs can be seen in [Table](#) , [Table 11](#), [Table 12](#), and [Table 13](#)). The starting doses (DL 1) will be 100% of the recommended adult dose of both durvalumab and tremelimumab administered as weight-adjusted doses. The doses and schedules are as follows:

1. Cycle 1 (durvalumab monotherapy): durvalumab 20 mg/kg
2. Cycles 2 to 5 (durvalumab in combination with tremelimumab): durvalumab 20 mg/kg and tremelimumab 1 mg/kg (4 cycles administered every 28 days)
3. From Cycle 6 onwards, treatment will continue until a discontinuation criterion is met, with durvalumab monotherapy administered at 20 mg/kg every 28 days.

From Cycle 2 onwards, a treatment delay of up to 14 days is permitted between consecutive cycles to manage any side-effects. If a treatment delay of more than 14 days is required, the start of the cycle that had to be delayed must be skipped until the planned Day 1 of the next cycle. No dose reductions are permitted.

[figure not shown]
The pediatric PK will be considered equivalent to the adult PK when the lower limit of the 80% CI of the pediatric exposure (as measured by the area under the plasma drug concentration-time curve from Day 0 to Day 28 [AUC_{0-28}]) is more than 50% of the adult exposure. Adequate exposure will be declared only if $\geq 80\%$ (5 of 6 patients at a dose level) achieve acceptable adult exposure PK, as defined. Durvalumab and tremelimumab will be escalated sequentially with durvalumab first followed by tremelimumab.

The degree of dose escalation at DLs 2 and 3 will be determined based on the review of all the safety and emerging PK data. It is anticipated that dose ranges of 24 to 40 mg/kg and 1.2 to 2 mg/kg for durvalumab and tremelimumab, respectively, will be explored in DLs 2 and 3 (the maximum dose of durvalumab that will be explored is 40 mg/kg).

Dose escalation will follow a modification of the standard 3 + 3 design. For Arm A (weight ≥ 35 kg), a total of 6 patients will be enrolled into this cohort; additional dose levels will only be evaluated if PK data indicate inadequate exposure to that of an adult. For Arm B (weight < 35 kg), if none of the 3 patients experience a DLT, then 3 additional patients will be treated at the next dose level. If 1 or more patients experience a DLT, the 3 additional patients (for a total of 6 patients) will be treated at the same dose level. Dose escalation will continue using the same rules-based approach until at least 2 patients among a cohort of 3 or 6 patients experience a DLT, at which time, DLT will be established.

Figure 2 Dose-finding: escalation schema

This figure shows the maximum doses for durvalumab at DLs 2 and 3 (40 mg/kg) and tremelimumab at DL 3 (2 mg/kg). Lower doses may be tested, depending on the obtained PK modeling data.

DL Dose level; NB Neuroblastoma; SARC-1 Osteosarcoma and Ewing sarcoma; SARC-2 Rhabdomyosarcoma, non-rhabdomyosarcoma, and other sarcomas; STO Solid tumor other.

As indicated in [Figure 2](#), DL 2 will assess an increased dose of durvalumab while holding tremelimumab dosing at 1 mg/kg.

[figure not shown]
If at DL 1, durvalumab exposure is adequate and tremelimumab exposure is too low, DL 2 can be skipped and tremelimumab alone will be escalated to DL 3 with durvalumab dosing staying at 20 mg/kg (100% of the recommended adult dose).

Furthermore, based on emerging PK, safety and tolerability data, intermediate DLs may also be tested.

De-escalation for toxicity may occur for durvalumab or tremelimumab to DL -1 with reduced doses of 15 mg/kg and 0.75 mg/kg, respectively (See [Figure 3](#)).

Figure 3 Dose-finding: de-escalation schema

DL Dose level

Assessments

During Cycle 1 and until Cycle 2 (Day 1), safety, tolerability, PK, and activity will be assessed as follows:

1. Encountered AEs will be reported and DLTs (defined in Section 4.1.2) will be identified
2. Four durvalumab PK samples (taken predose and end-of -infusion on Day 1 and on Day 8 and Day 15) will be obtained and
3. Three samples will be taken on Day 1 (pre- and postdose) and Day 8 to determine CCI.

During Cycle 2, safety, tolerability, PK, and activity will be assessed as follows:

1. Encountered AEs will be reported and DLTs will be identified
2. Two durvalumab PK samples (taken predose and at the end of infusion on Day 1) will be obtained
3. Four tremelimumab PK samples (taken predose and end-of -infusion on Day 1 and on Day 8 and Day 15) will be obtained and
4. One sample will be taken on Day 1 prior to dosing of tremelimumab to determine CCI.

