- Grade 3 hypothyroidism adequately treated with hormone replacement therapy.
- Grade 3 inflammatory reaction attributed to a local antitumor response (eg, inflammatory reaction at sites of metastatic disease, lymph nodes, etc.).
- Concurrent vitiligo or alopecia of any AE grade.
- Grade 3 infusion-related reaction (first occurrence and in the absence of steroid prophylaxis) that resolves within 6 hours with appropriate clinical management.
- Grade 3 fever (fever greater than 40°C [$>104^{\circ}\text{F}$] for $\leq 24\text{h}$ in duration).
- Any grade lymphopenia.
- Isolated Grade 3 electrolyte abnormalities that are not associated with clinical signs or symptoms and are reversed with appropriate maximal medical intervention (including supplementation) within 7 days of initiating supplementation.

Immune-related adverse events are defined as AEs of immune nature (ie, inflammatory) in the absence of a clear alternative etiology. In the absence of clinical abnormality, repeat laboratory testing must be conducted to confirm significant laboratory findings prior to designation as a DLT.

Guiding principles:

1. While the rules outlined above dictate the classification of AEs as DLTs, any other AEs that are observed during the observation period may be defined as a DLT in consultation with the DRC; after having taken into consideration the emerging safety profile of durvalumab and tremelimumab.
2. The NCI CTCAE (version 5.0) will be used for AEs reporting and its severity will be graded on a scale from 1 to 5 provided for each AE term.
3. An immune-mediated AE is defined as an AE that is associated with exposure to durvalumab or/and tremelimumab and is consistent with an immune-mediated mechanism of action after alternate etiologies have been considered and excluded.

4. In the absence of clinical findings, repeat laboratory testing must be conducted to confirm the clinical significance of abnormal laboratory test result before it is classified as a DLT.

Patient dosing or study enrollment may be halted in the dose-finding phase until the toxicity data can be further studied. If DLTs occur in $\geq 2/6$ patients on a given cohort, enrollment will be placed on hold and the DRC will be required to fully evaluate the available information prior to further patient enrollment. Upon review, a decision will be made to resume, stop or modify the study. If ≥ 2 DLTs occur at DL -1, the study may be prematurely stopped.

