4.1.3 Determining a recommended Phase II dose

A DRC will be established prior to the initiation of the study to review all the data, with a primary emphasis on safety and PK, to establish RP2D to be further explored in the dose-expansion phase of the study. Dose escalation decisions and determination of RP2D will mainly consider safety assessments from at least 3 patients followed up for 4 cycles, to include a single cycle of durvalumab and 3 cycles of the combination of durvalumab and tremelimumab (for a total of 120 days). More details on the DRC constitution are described in Section 9.6.1.

The key considerations to be followed by the DRC during the dose-finding phase of the study are outlined in [Table 8](#).

Table 8 Key considerations for dose escalation decisions

#DLTs	Pharmacokinetics	Decision/Outcome
0 out of 3-5	Equivalent to adult exposure (5 out of 6 patients) Less than 80% of adult exposure (≤ 2 patients)	Declare tolerated and observe for 4 cycles, and if < 2 patients with DLTs are observed during the first 4 cycles of study drug, enter dose-expansion stage Declare tolerated and move to next DL
OR 1 out of 6		
1 out of 3		Increase number of patients to 6
≥ 2		Declare not tolerated; if observed on DL 1, move to DL -1

DL Dose level; DLT Dose-limiting toxicity.

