9.6.1 Data Review Committee

A DRC will be established prior to the initiation of the study and will review the safety and PK data. The DRC membership will comprise of participating Investigators and representatives from both AstraZeneca (Pharmacovigilance Scientists for durvalumab and tremelimumab, PK Scientist, Study Physician and Biostatistician) and IQVIA (Study Physician, Safety Physician and Biostatistician). On a case-by-case basis, the DRC may also seek advice from pediatric oncologists with the required site specialization expertise.

Working rules, including the timing of planned meetings, will be described in the DRC charter. In summary, recommendations and decisions will be made through consensus of opinion amongst the DRC members with all decisions being documented and distributed to DRC members. Additionally, 'ad-hoc' DRC meetings may be convened, if required, anytime during the conduct of the study.

The key tasks of the DRC members will be to review the data recorded in the clinical database in conjunction with the PK data to:

1. Determine whether DLTs have occurred
2. Decide whether additional patients should be added to a cohort
3. Recommend de-escalating a dose that was poorly tolerated or escalating a dose if PK exposures inferior to those observed in adults, were achieved
4. Declare that dose finding is complete

5. Recommended a RP2D to be explored in the dose-expansion phase of the study
6. Perform a benefit/risk assessment at the completion of safety data analysis for children <1 year old prior to enrolling a patient less than 1 year old; notify local health authority of decision, if applicable, as per local requirements
7. Put enrollment on hold
8. End the study.

During the dose-expansion phase, the DRC will review safety, tolerability, PK, and efficacy data to make consensual decisions on cohort expansion or closure, and end the study, among others.

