A Data Review Committee (DRC) will be established prior to the initiation of the study to make decisions on dose escalations and determination of a recommended phase 2 dose (RP2D) to be further explored in the dose-expansion phase.

Dose escalation decisions will aim to identify the RP2D for durvalumab and tremelimumab in combination. Dose escalation decisions and determination of RP2D will mainly consider safety and PK information obtained from Cycle 1 (durvalumab monotherapy) and Cycle 2 (first administration of durvalumab and tremelimumab combined). This includes assessment of pre-defined dose-limiting toxicities (DLTs) in the first 2 cycles.

A de-escalation step may occur for durvalumab or/and tremelimumab, with reduced doses of 15 mg/kg and 0.75 mg/kg, respectively, if dose level 1 is considered not tolerated. Furthermore, if exposure of durvalumab or/and tremelimumab proves inadequate, intermediate dose levels may also be tested.

At least 1 patient representing each of the following pediatric age subsets will be enrolled: birth to 5 years, 6 to 11 years and 12 to <18 years. In addition, 3 patients older than 2 years of age must be treated with durvalumab in combination with tremelimumab and clear the DLT period and have been evaluated by the DRC before children less than 2 years old may be enrolled in the dose-finding phase.

[figure not shown]
The key considerations to be followed by the DRC during the dose-finding phase of the study are outlined in [Table 1](#):

Table 1 Key considerations for DRC

#DLTs	PK	Decision/Outcome
0 out of 3-5	Equivalent to adult exposure (5 out of 6 patients)	Declare tolerated and observed for 4 cycles, and if <2 patients with DLTs are observed during the first 4 cycles of study drug, enter dose-expansion stage
OR		
1 out of 6	<80% of adult exposure (≤2 patients)	Declare tolerated and move to next dose level.
1 out of 3		Increase number of patients to 6.
≥2		Declare not tolerated; if observed on dose level 1, move to dose level -1 (see Figure 2).

DLT dose limiting toxicity; DRC data review committee; PK pharmacokinetics.

Figure 2 Dose-finding: de-escalation schema

DL dose level.

A separate document (a DRC charter) will be created to detail all key tasks, working rules and timing of meetings of the DRC committee.

Dose-expansion phase

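### Protocol Section 4.1.1 expands an Arm B dose level after any number of DLTs in the first three children, although Table 8 and SAP Table 1 fail the dose at two

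*Protocol*

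**What the plan says.** The dose-finding phase uses a modified 3 + 3 design with two weight-based arms. Arm A (35 kg and above) enrolls a fixed six patients, so the point concerns only Arm B (under 35 kg).

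Protocol Section 4.1.1 gives the Arm B rules in three consecutive sentences:

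- No DLT in the first three: "if none of the 3 patients experience a DLT, then 3 additional patients will be treated at the next dose level".
- Any DLT in the first three: "If 1 or more patients experience a DLT, the 3 additional patients (for a total of 6 patients) will be treated", with the dose unchanged.
- Escalation then continues "until at least 2 patients among a cohort of 3 or 6 patients experience a DLT".

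Protocol Section 4.1.3, Table 8, sets out what the DRC is to follow. Its row for one DLT in three raises the number to six. Its row for two or more, which carries no denominator, reads: "Declare not tolerated; if observed on DL 1, move to DL -1". SAP Section 1.2, Table 1, has the same rows; its last reads: "Declare not tolerated; if observed on dose level 1, move to dose level -1".

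Protocol Section 4.1.2 adds a mandatory hold. Its threshold is two or more of six "patients on a given cohort, enrollment will be placed on hold and the DRC will be required to fully evaluate" the data before enrollment resumes. Among the DRC's tasks, Section 9.6.1 lists: "Decide whether additional patients should be added to a cohort".

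**The concern.** The expansion sentence sets a lower limit on DLTs but no upper one. With three children treated, one or more covers 1/3, 2/3 and 3/3. At 2/3 or 3/3, Section 4.1.1 tells the site to treat three more at the same dose, while Table 8 and SAP Table 1 say that the dose has failed.

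These would be children under 35 kg, in the arm where higher doses are expected to be needed (up to 40 mg/kg durvalumab and 2 mg/kg tremelimumab). A DLT as defined in Section 4.1.2 can be a Grade 5 event. What is at stake is avoidable exposure at a dose that the decision table already rejects.

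**Working it through.** **The plan's own figures.** Section 9.2 states dose-finding sizes only and gives no operating characteristics for the escalation rule. The sizes reproduce:

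- Minimum: 2 arms × 1 level × 6 = 12.
- Maximum evaluable: 2 arms × 3 levels × 6 = 36.
- Maximum enrolled with 20% replaced: 36 / (1 − 0.20) = 45.

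Both maxima already assume six per level, so neither depends on which expansion rule applies.

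**The rules side by side, by DLTs in the first three Arm B children.**

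| DLTs | 4.1.1 expansion sentences, literal | Table 8 and SAP Table 1 |
|---|---|---|
| 0/3 | escalate | tolerated; next step depends on exposure |
| 1/3 | three more, same dose | three more, same dose |
| 2/3 or 3/3 | three more, same dose | not tolerated |

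On expansion, the rules part only in the last row.

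**Can the extra children change the verdict?** No. Starting from 2/3 or 3/3, the total after six is at least 2/6, which fails. Taking the DLT rules alone, the probability of declaring a level tolerated is therefore the same under both:

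P(tolerated) = (1 − p)³ + 3p(1 − p)² × (1 − p)³

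**How often does the conflict arise?** The documents give no true DLT rate p, so the values below are assumptions. DLTs are taken as independent between children.

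- P(two or more in three) = 3p²(1 − p) + p³
- Expected extra children per dose level, if the literal rule is followed = 3 × P(two or more in three)
- P(expand), literal = 1 − (1 − p)³
- P(expand), Table 8 = 3p(1 − p)²

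| Assumed p | P(≥2 of 3) | Expected extra children | P(expand), literal | P(expand), Table 8 | P(tolerated), both |
|---|---|---|---|---|---|
| 0.05 | 0.007 | 0.02 | 0.143 | 0.135 | 0.973 |
| 0.10 | 0.028 | 0.08 | 0.271 | 0.243 | 0.906 |
| 0.15 | 0.061 | 0.18 | 0.386 | 0.325 | 0.814 |
| 0.20 | 0.104 | 0.31 | 0.488 | 0.384 | 0.709 |
| 0.33 | 0.255 | 0.76 | 0.699 | 0.444 | 0.434 |
| 0.50 | 0.500 | 1.50 | 0.875 | 0.375 | 0.172 |

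Example at p = 0.20: 3 × 0.04 × 0.80 + 0.008 = 0.104, and 3 × 0.104 = 0.312.

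If the conflict arises and three more are treated, the expected number of further DLTs among them is 3p: 0.3 at p = 0.10, 0.6 at 0.20 and 1.5 at 0.50.

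**Does the Section 4.1.2 hold close the gap?** Not explicitly. Its threshold is written for six patients and does not mention 2/3.

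**The case against.** The strongest reply is that the documents, taken together, already settle the matter. The sentence after the disputed one names a cohort of three as well as six, which would serve no purpose if 2/3 always went on to six. Table 8 is what the DRC is told to follow, and the DRC decides on adding patients. Two DLTs in three also guarantee at least two in six, so a sensible reader would apply the hold at once, and Section 4.1.2 separately allows dosing or enrollment to be halted at discretion. On this view the phrase is a drafting slip: nobody chose to expand after 2/3.

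Much of this stands. The intent is clear from the tables, and the extra exposure occurs only if the DRC does not act on them. The high assumed rates have no support in the documents for the starting dose: the pediatric durvalumab monotherapy study reports no DLTs in 11 evaluable patients, and children under 35 kg are predicted to have lower exposure than adults. The combination, however, had not been studied in children, so high rates cannot be excluded.

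It does not make the sentence right. The following sentence governs when escalation ends; it does not withdraw the instruction to treat three more at the same level. Calling the design modified does not help either, since nothing presents expansion after 2/3 as the modification and both tables contradict it. Nor does the exposure criterion (five of six patients) justify it, because a dose that is not tolerated is not carried forward.

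The version history refers to results from the dose-finding phase, so Arm B enrollment may already be over. The correction would then mainly serve accurate reporting of the rule used, and any reuse of the text.

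**Conclusion.** The concern holds. The Arm B expansion rule in Section 4.1.1 has the wrong threshold and conflicts with Table 8, SAP Table 1 and its own next sentence. No tolerability verdict, sample-size maximum or analysis depends on it; the consequence is limited to exposure.

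The chance that the conflicting wording comes into play at a given dose level runs from 0.007 at an assumed DLT rate of 5% to 0.50 at 50%. That is not the chance of extra exposure, because the DRC may stop enrollment first. The expected 0.02 to 1.5 extra children per level applies only if the literal rule is followed. The point should be corrected: the sentence is an operative safety rule in a pediatric trial, and following it as written could bring no gain for the tolerability decision.

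**What to change.** In Protocol Section 4.1.1, replace the open-ended condition with two explicit ones:

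- Exactly one DLT among the first three Arm B patients: enroll three more at that dose level.
- Two or more DLTs, whether among three or among six: the dose level is not tolerated and no further patients are treated at it.

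In Section 4.1.2, extend the mandatory hold to two or more DLTs in a cohort of three or six. This second edit is a clarification that brings the hold into line with Table 8.

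The cost is one phrase in each section. Table 8, SAP Table 1, the 12/36/45 sample sizes and the error rates of the expansion phase do not change.

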1.2 Study design

This is an open-label, non-randomized, international, multicenter study investigating durvalumab in combination with tremelimumab (q4w for 4 cycles only) followed by durvalumab monotherapy (q4w) in pediatric patients from birth to <18 years of age with relapsed or refractory malignant solid tumors. Each treatment cycle is 28 days.

The study will be conducted in 2 sequential phases; a dose-finding phase (Phase I) followed by a disease specific dose-expansion phase (Phase II). The purpose of this study is to identify the recommended Phase II dose (RP2D) that will be taken forward to determine preliminary antitumor activity of durvalumab in combination with tremelimumab in solid malignant tumors, using disease specific response criteria.

Dose-finding phase

The dose-finding phase of the study will be conducted using a 3 + 3 design to determine whether durvalumab and tremelimumab can be administered safely in children and if adult exposures can be achieved. Pediatric patients with relapsed or refractory solid malignant tumors including osteosarcoma and Ewing sarcoma (SARC-1), rhabdomyosarcoma, non-rhabdomyosarcoma, and other sarcomas (SARC-2), neuroblastoma (NB), and other solid tumors (STO), will be enrolled in 2 arms based on patient weight:

[figure not shown]
- Arm A: patients weighing ≥ 35 kg
- Arm B: patients weighing < 35 kg

Three dose levels may be explored in each of the arms as outlined in [Figure 1](#). Dose level 1 will be 100% of the recommended adult dose of both durvalumab and tremelimumab administered as weight-adjusted doses. The doses and schedules are as follows:

- 1 Cycle 1 (durvalumab monotherapy): durvalumab 20 mg/kg
- 2 Cycles 2 to 5 (durvalumab in combination with tremelimumab): durvalumab 20 mg/kg and tremelimumab 1 mg/kg [4 cycles administered every 28 days]
- 3 From Cycle 6 onwards, treatment will continue until a discontinuation criterion is met, with durvalumab monotherapy administered at 20 mg/kg q4w.

At least one day between first patient and subsequent patients dosed at each dose-level is required.

Figure 1 Dose levels – Dose-finding phase

This figure shows the maximum doses for durvalumab at DLs 2 and 3 (40 mg/kg) and tremelimumab at DL 3 (2 mg/kg). Lower doses may be tested, depending on the obtained PK modeling data.

DL Dose level; NB Neuroblastoma; SARC-1 Osteosarcoma and Ewing sarcoma; SARC-2 Rhabdomyosarcoma, non-rhabdomyosarcoma, and other sarcomas; STO Solid tumor other.

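### Protocol 4.1.1 expands an Arm B cohort to 6 after any DLT in the first 3, but Table 8 and SAP Table 1 expand only after exactly 1: a minor inconsistency in a safety threshold

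*Protocol*

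**What the plan says.** Protocol 4.1.1 gives the Arm B rule in three steps. With no DLT in the first 3 patients, the next 3 go to the next dose level. Then: "If 1 or more patients experience a DLT, the 3 additional patients (for a total of 6 patients) will be treated at the same dose". Escalation goes on "until at least 2 patients among a cohort of 3 or 6 patients experience a DLT, at which time, DLT will be established".

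Protocol 4.1.3 introduces Table 8 with "The key considerations to be followed by the DRC during the dose-finding phase of the study are outlined in" that table. Table 8 raises the cohort to 6 only in its row for 1 of 3. Its row for two or more DLTs reads "Declare not tolerated; if observed on DL 1, move to DL -1".

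SAP 1.2 says "The dose-finding phase of the study will be conducted using a 3 + 3 design" and does not carry the 4.1.1 sentence. Its Table 1 repeats the protocol's decision table, including "Declare not tolerated; if observed on dose level 1, move to dose level -1" for two or more DLTs.

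Protocol 4.1.2 adds two safeguards. One is discretionary: dosing or enrollment may be stopped during dose finding while toxicity data are studied, with no denominator given. The other is mandatory and is written for DLTs in at least 2 of 6 patients "on a given cohort, enrollment will be placed on hold and the DRC will be required to fully evaluate the available information". Protocol 9.6.1 makes adding patients to a cohort a DRC decision.

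**The concern.** The sentence before the expansion rule covers 0 of 3, so the rule itself covers 1, 2 and 3 of 3. For 2 or 3 of 3 it tells the site to treat three more children at that dose. The decision tables say to stop and, at dose level 1, to move down.

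At stake is a written safety threshold for the lower-weight arm, for a combination that protocol 2.3.2.3 says had not been evaluated in children. Someone who reads only 4.1.1 gets a different rule from the one the DRC is told to follow. If the literal rule were applied, the DLT percentage by dose level (SAP 4.2.3.1) would shift as well.

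**Working it through.** **Planned numbers first.** Protocol 9.2 gives a minimum of 12, a maximum of 36 evaluable and a maximum of 45 enrolled.

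- Minimum: 6 per level × 1 level × 2 arms = 12.
- Maximum evaluable: 6 × 3 × 2 = 36.
- Enrolled, allowing for 20% non-evaluable: 36 / (1 − 0.20) = 45.

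All three reproduce. They do not depend on which text is followed, because a level reaches 6 through the 1-of-3 route in any case. The Arm B maximum is 6 × 3 = 18 evaluable either way.

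**The two rules side by side (Arm B, first 3 patients).**

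| DLTs in first 3 | 4.1.1 read literally | Table 8 / SAP Table 1 |
|---|---|---|
| 0 | 3 patients at next level | tolerated; next step depends on PK |
| 1 | 3 more at same level | increase to 6 |
| 2 or 3 | 3 more at same level | not tolerated; from level 1, move to level −1 |

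They differ only in the last row. The row for two or more DLTs in the tables has no denominator. The phrase in 4.1.1 about a cohort of 3 or 6 shows that a cohort can fail at 3. That phrase alone only ends escalation; it is the tables that rule out expansion at 2 of 3.

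**Does the verdict change?** A level is tolerated at 0/3 or at no more than 1/6. Starting from 2/3 or 3/3, the count after expansion is still at least 2 of 6, so the level fails under both rules. Under both,

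P(tolerated) = (1 − p)³ + 3p(1 − p)² × (1 − p)³.

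This equality is algebraic and holds at every DLT rate p.

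**How often do the rules diverge, and at what cost?** The documents give no DLT rate for the combination in children, so p is an assumption shown as a range.

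- Divergence at a level: q = P(at least 2 of 3) = 3p²(1 − p) + p³.
- Mean extra children per level if the literal text were always followed: 3q.
- Mean extra DLTs among them: 3pq.

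| Assumed p | q | 3q | 3pq | P(tolerated), both rules |
|---|---|---|---|---|
| 10% | 0.027 + 0.001 = 2.8% | 0.08 | 0.01 | 0.906 |
| 20% | 0.096 + 0.008 = 10.4% | 0.31 | 0.06 | 0.709 |
| 30% | 0.189 + 0.027 = 21.6% | 0.65 | 0.19 | 0.494 |
| 50% | 0.375 + 0.125 = 50% | 1.50 | 0.75 | 0.172 |

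**Reported DLT percentage.** A level stopped at 2/3 would be reported as 67%. After literal expansion it would be between 2/6 (33%) and 5/6 (83%).

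**The case against.** The best defence is that the documents already settle the matter. The next sentence of 4.1.1 makes 2 DLTs in a cohort of 3 the end of escalation. The DRC decides on added patients and is told to follow Table 8. The discretionary halt in 4.1.2 has no denominator, so it covers 2/3 and 3/3. Even the mandatory hold, sensibly read, would stop enrollment before a fourth patient, since 2 DLTs cannot become fewer. Figures 2 and 3 were not visible in the text I worked from, and the DRC charter is a separate document; either may state the trigger correctly. Dose finding is also probably over: protocol 4.1 puts the last visit for the final analysis at about Q1 2023.

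Most of this stands, and it keeps the point minor. It does not make the sentence right. Nor does the protocol's description of the design as a modified 3 + 3 explain it: no reason is given for expanding after 2/3 or 3/3, and doing so cannot inform the dose decision.

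A reader might also infer that the mandatory hold leaves a safety gap that calls for rewriting 4.1.2. The documents do not support that. The hold does not name a cohort of 3, but the discretionary halt and Table 8 cover the case.

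**Conclusion.** Protocol 4.1.1 is wrong as written. It is a minor internal inconsistency, and the intended trigger, exactly 1 of 3, is clear from Table 8 and SAP Table 1. Followed literally, it would expose up to 3 more children at an Arm B level already not tolerated, with no possible change in the verdict. The chance of that situation at a level is 2.8% to 50% over assumed DLT rates of 10% to 50%. The mean of 0.08 to 1.50 extra children per level is an upper bound, because it supposes that Table 8 is ignored every time.

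A reader might infer that the recommended Phase II dose or the sample size is compromised. Neither is: the tolerated decision is identical under both rules, and 12/36/45 is unchanged. Only realised enrollment could be 3 higher at a failed level.

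A reader might also narrow the range to 10–20%, citing no DLTs in 11 evaluable children (protocol 4.3.1.2) and related SAEs in about 15% of adults (2.3.2.3). Those figures do not justify it. The first is durvalumab alone every 14 days, and its exact one-sided 95% upper bound, 1 − 0.05^(1/11) = 23.8%, already exceeds 20%. The second counts adult SAEs, not DLTs in a 56-day window.

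No document says that 2 or more of the first 3 patients had a DLT at any Arm B level.

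**What to change.** In protocol 4.1.1, change the condition for expansion to *If exactly 1 of the 3 patients experiences a DLT*, and add: *If 2 or more of the first 3 patients experience a DLT, the dose level is declared not tolerated and no further patients are treated at it (Table 8).*

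Table 8, SAP Table 1 and the planned numbers need no change. The hold in 4.1.2 needs no rewrite. If it is edited anyway, only add *or ≥2/3* beside the existing 2-of-6 trigger. It should not be capped at 6 patients or limited so as to leave out backfilled patients: 4.1.1 says "cohorts may also be backfilled to provide further assessment of safety and PK in specific age groups", and DLTs in those children should still count towards a hold.

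If dose finding is complete, state in the CSR which rule was applied at any Arm B level with 2 or more DLTs in the first 3.

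The cost is two sentences in the protocol, or one in the CSR, and no extra patients.
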